### **7.3 Safety Analysis population**

The Safety Analysis population will comprise all subjects who received an infusion of IMP. All analyses using the Safety Analysis population will group subjects according to the treatment actually received.

The Safety Analysis population will be used for the safety analyses.

## **8 General issues for statistical analysis**

No formal statistical hypothesis testing will be performed. All endpoints will be summarized with descriptive statistics and presented individually in listings.

### **8.1 Statistical Analysis and Tabulation Software**

Below are the software and its versions used in this study.

	Software and Versions
OS	Microsoft Windows 10
Statistical Analysis Software	SAS Ver.9.4 or later (SAS Institute Inc., Cary, North Carolina, United States)
Tabulation Software	Microsoft Word 2016 or later
WinNonlin	WinNonlin Ver.8.0 or later

### **8.2 Dictionaries**

Below are the dictionaries used in this study.

Category	Dictionary	Remarks
Adverse Events	MedDRA Version: refer to SDTM define.xml	
 
The System Organ Class (SOC) for major system organ class name will be applied.
 
The Preferred Term (PT) for adverse events name will be applied.
 
Adverse events will be sorted by SOC and PT.
 

Medical History	MedDRA Version: refer to SDTM define.xml	
 
The System Organ Class (SOC) for major system organ class name will be applied.
 
The Preferred Term (PT) for medical histories name will be applied.
 

Prior/Concomitant Medications	WHO drug dictionary (Version September 2020)	
 
The generic medication name will be applied.
 
Medical history will be displayed by generic medication name.
 

Abbreviations: WHO, World Health Organization.

## 8.3 Analysis Methods

### 8.3.1 Descriptive statistics

Continuous data will be summarized using descriptive statistics: the number of subjects (N), arithmetic mean, standard deviation (SD), median, minimum and maximum.

In PK analysis, geometric mean (geo mean), coefficient of variation (CV %) and 95 % confidence intervals of geo mean are also presented. CV % and Geo mean are calculated using the following formula:

$$CV = (\text{standard deviation}) / (\text{arithmetic mean}) * 100$$

$$\text{Geometric mean} = \exp \left[ \frac{\sum_{i=1}^n \log X_i}{n} \right] = \sqrt[n]{\prod_{i=1}^n X_i}$$

### 8.3.2 Percentages

Percentage is calculated using the following formula (unless otherwise indicated):

$$\text{Percentage (\%)} = \frac{\text{the number of applicable subjects}}{\text{the number of subjects within the treatment group for the population of interest}} \times 100$$

Percentages will be suppressed when the count is zero, however the category will still be displayed.

## 8.4 Handling of Data

### 8.4.1 Calculation Method of Number of Days

Number of days is calculated using the following formulas:

- Post-treatment study day: [The date of a respective event] - [The date of IMP administration] +1
- Pre-treatment study day: [The date of a respective event during pre-dosing time] - [The date of IMP administration]

### 8.4.2 Calculation of Age

Age is calculated using the birth date.

- Age at the time of informed consent will be calculated using the following formula (unless otherwise indicated):

$$\text{Age (Years)} = \frac{(\text{Informed Consent Obtained Date} - \text{Birth Date})}{365.25}$$

### 8.4.3 Visit Windows

The visit windows for PK and PD assessments are displayed in Table 1, for Vital signs in Table 2 and for other assessments in Table 3. The analysis time points, based on the visit windows, will be used for analysis. In addition, let the IMP administration date be Day 1.

For descriptive statistics, in the case a parameter is not available on the specified analysis timepoint, the visit window is to be applied. Priority will be given to scheduled visits; unscheduled visits will be used if no scheduled visits occurred within the analysis visit window.

If there is more than one observation during the visit window, a value will be selected as follows: the value closest to the actual analysis timepoint in question (eCRF) will be chosen first. In the case that there are 2 values equidistant to the analysis timepoint of interest, the observation that is before the analysis timepoint in question (eCRF) will be selected. In the case of 2 or more measurements on the same date, the earliest measurement will be selected.

**Table 1** Visit Window of pharmacokinetic and pharmacodynamic assessment

Analysis time point		Visit Window	Pharmacokinetics	Pharmacodynamics
Day 1	Preinfusion	Before IMP administration	X	X
	1 hr	55 min to < 65 min	X a)	X
	2 hr	1 hr 55 min to < 2 hrs 5 min	X	X
	4 hr	3.75 hr to <4.25 hr	X	X
	8 hr	7.5 hr to <8.5 hr	X	X
	10 hr	9.5 hr to <10.5 hr	X	X
Day 2		Day 2	X	X
Day 3		Within Day 3	X	X
Day 5		Within Day 5	X	X
Day 8		Within Day 8	X	X
Follow-up Week 2		Day 12 to Day 16	X	X
Follow-up Week 4		Day 26 to Day 30	X	X
Follow-up Week 6		Day 40 to Day 44	X	X
Follow-up Week 8		Day 54 to Day 58	X	
Follow-up Week 10		Day 68 to Day 72	X	
Follow-up Week 12		Day 82 to Day 86	X	
Study Completion Visit (Week 14)		Day 96 to Day 100	X	X
Withdrawal (WD)		When the subject is withdrawn	X	X

a) At end of infusion.

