6.1 Overall study design and plan

This is a randomized, placebo-controlled and double-blinded study to evaluate the PK, PD and safety of a single dose (1 mg/kg) of emapalumab in adult healthy Japanese subjects, performed in Japan. The subjects, 8 in total, will be randomized to receive either emapalumab or matching placebo in a 3:1 ratio (emapalumab: placebo).

Figure 1 shows the study design.

Study subjects will be screened within 21 days prior to administration of investigational medicinal products (IMP). An additional visit will take place within 96 hours prior to IMP infusion for collection a PCR test for SARS-CoV-19. Eligible subjects will be admitted to the clinical unit the day before drug administration (Study Day -1). On Day 1 of the admission period subjects will receive a single dose of emapalumab (1 mg/kg) or placebo administered as a 1-hour infusion. Subjects will be discharged from the unit on Day 8. PK samples will be collected for up to week 14 in order to measure the emapalumab serum levels during at least 3 times the terminal half-life (a total of approximately 3 months). All subjects will be followed-up on regular visits for a minimum of 14 weeks after single infusion of emapalumab. In addition, any subject with ongoing SAEs at study completion will be followed-up until resolution.

Figure 1 **Study Design**

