6.7.1.4 Follow-Up visits (Study W2, W4, W6, W8, W10, W12)

All assessments and procedures will be performed according to the schedule of events (Table 4). The time window for the visits on week 2, 4, 6, 8, 10, and 12 is \pm 2 days.

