V ss	
Steady state volume of distribution
 
Calculate from the following formula in subjects whose <math>\lambda_z</math> can be calculated.
 $V_{ss} = CL \times MRT_{inf}$ 
Vss is calculated using dose level (mg/kg) and actual dose (mg).
	L	3 significant figures
MRT last	
Average residence time from the start of infusion to the final blood collection time
 $= \frac{AUMC_{last}}{AUC_{last}} - \frac{TI}{2}$ 
TI :Duration of infusion
	h	3 significant figures
MRT inf	
Average residence time from start of infusion to infinite time
 $= \frac{AUMC_{inf\_calc}}{AUC_{INF\_calc}} - \frac{TI}{2}$ 
TI :Duration of infusion
	h	3 significant figures

Subjects will be excluded from the PK analysis if their data do not allow for accurate assessment of the PK (e.g. incomplete administration of the study drug; subject vomited after receiving study drug; missing information of dosing and sampling times; concentration data not sufficient for PK parameter calculation).Following rules will be applied for descriptive statistics.

- Lower Limit of Quantification (LLOQ) will be substituted with 0.
- The number of subject displayed as "N" on summary tables will be the number of subject whose serum concentrations are measured (include LLOQ) or PK parameters are calculated.
- When the time of blood collection is outside the time windows, the relevant serum concentration will be listed but excluded from the calculation of summary statistics.

**Table 5** List of compound and lower limit of quantification

Compound	Unit	Lower Limit of Quantification	Rounding Digit
Emapalumab	ug/L	62.5 ug/L	0.01

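### SAP follow-up windows may sit one day early: if Week k means k weeks after the infusion, a compliant +2-day visit falls outside and its concentration leaves the by-visit PK summaries

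*SAP*

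**What the plan says.** SAP 8.4.3 fixes the day count with "let the IMP administration date be Day 1", and SAP 8.4.1 gives the same count as a formula, "Post-treatment study day: [The date of a respective event] - [The date of IMP administration] +1". There is no Day 0.

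SAP Table 1 sets the Week 2 window at "Day 12 to Day 16" and moves on in 14-day steps to Week 14 at "Day 96 to Day 100". Tables 2 and 3 use the same windows for vital signs, laboratory tests, ADA and the other assessments at the weeks they cover.

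On the site side, the sentence in Protocol 6.7.1.4 that begins "The time window for the visits on week 2, 4, 6, 8, 10, and 12 is" ends with ±2 days, and Protocol 6.7.1.5 gives ±2 days for Week 14. Protocol 6.1 describes follow-up "for a minimum of 14 weeks after single infusion of emapalumab", and SAP 4.1 says nearly the same.

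For a PK sample drawn outside its window, the rules that follow the parameter list in SAP 14.1 say that "the relevant serum concentration will be listed but excluded from the calculation of summary statistics".

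The text of neither document assigns a nominal study day to any Week visit. The design figure was not available to check.

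**The concern.** The site schedules visits by the protocol's week labels and ±2-day tolerance. The SAP assigns them by study day. If the two count from origins one day apart, a sample taken on time by the protocol can be out of window in the analysis, while one taken too early by the protocol is accepted.

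The exposed output is the concentration summary by visit (SAP 14.1.1) and probably the mean ± SD plot (SAP 14.1.2), which use the same analysis time points. Only six subjects receive emapalumab, so one excluded value leaves five at that visit.

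**Working it through.** **Inputs.** Day origin and formula: SAP 8.4.1 and 8.4.3. Windows: SAP Table 1. Tolerance: Protocol 6.7.1.4 and 6.7.1.5. Active subjects: 6 (Protocol 6.6). Follow-up PK visits: 7 (Weeks 2, 4, 6, 8, 10, 12 and 14 in SAP Table 1). Terminal half-life: 25.4 days (Protocol 4.1.2.3) or around 22 days (Protocol 6.6.3). CV: within 30% for Cmax and AUC in the earlier study (SAP 6).

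**Step 1: reproduce the SAP windows.** Taking Week k as Study Day 7k, with window 7k ± 2, reproduces all seven. Taking Week k as 7k days after dosing, the nominal day is 7k + 1 and the window is 7k + 1 ± 2. This reproduces none of them.

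| Visit | SAP window | SAP window, days after dosing | 7k days after dosing, as study day | ±2 window on that day | Compliant day outside the SAP window |
|---|---|---|---|---|---|
| Week 2 | 12–16 | 11–15 | 15 | 13–17 | 17 |
| Week 4 | 26–30 | 25–29 | 29 | 27–31 | 31 |
| Week 6 | 40–44 | 39–43 | 43 | 41–45 | 45 |
| Week 8 | 54–58 | 53–57 | 57 | 55–59 | 59 |
| Week 10 | 68–72 | 67–71 | 71 | 69–73 | 73 |
| Week 12 | 82–86 | 81–85 | 85 | 83–87 | 87 |
| Week 14 | 96–100 | 95–99 | 99 | 97–101 | 101 |

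Under the second reading every SAP window covers -3 to +1 days. The +2-day visit is the only compliant one excluded, and a -3-day visit is accepted. The Week 14 centre, Day 98, is 97 days after dosing, one day short of 14 weeks.

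**Step 2: expected loss.** Active-arm follow-up PK samples: 6 × 7 = 42. Let p be the chance that a visit falls at +2 days. The documents give no value for p. The last column assumes that subjects attend independently.

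| p | Expected samples lost, 42p | Chance that a given visit has fewer than 6 values, 1 - (1 - p)^6 |
|---|---|---|
| 0 | 0 | 0 |
| 0.05 | 2.1 | 26% |
| 0.20 (uniform over five days) | 8.4 | 74% |

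**Step 3: what one exclusion costs.** Assume that the 30% upper figure for Cmax and AUC also applies to by-visit concentrations. Dropping one of six values at random then typically moves the mean by 0.30 × √(1.2)/6 ≈ 5%. The multiplier of a t-based 95% interval goes from 2.571/√6 = 1.05 to 2.776/√5 = 1.24, about 18% wider.

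Keeping a sample drawn two days late changes that one value by 1 - 2^(-2/25.4) = 5.3%, or 1 - 2^(-2/22) = 6.1% with the shorter half-life. That is about 1% of a six-subject mean. One day changes it by 2.7% to 3.1%.

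**The case against.** The strongest reply is that the windows are coherent as they stand. All seven equal Study Day 7k ± 2, and no text says that Week k is 7k days after dosing. The support for that reading is suggestive only:

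- The 14-week minimum cannot be literal, because the protocol also allows Week 14 two days early.
- Day 8 is seven days after dosing under the SAP count, but neither document labels it Week 1.
- The protocol counts days loosely elsewhere: Section 6.3.2 has subjects in hospital until 8 days after treatment, while Section 6.1 discharges them on Day 8.

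This stands, and it makes the point conditional.

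A reader might also infer that the primary PK parameters are affected. They are not. Protocol 6.7.5.2 and SAP 14.1 calculate them from actual times, SAP 14.1.3 plots individual profiles at actual times, and every concentration is listed.

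A reader might further infer that PD, laboratory, vital-sign and ADA values are dropped too. The SAP does not say so. Its exclusion rule covers serum concentrations only, and SAP 8.4.3 can be read as using the window only when no value exists at the planned time. For these data a +2-day value merely lacks a clearly assigned analysis visit. The Week 14 ADA sample, the only planned one after dosing, is an example.

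The reply does not remove the PK point. The exclusion rule in SAP 14.1 is explicit, and the 8.4.3 fallback sends a +2-day sample back to the same window it has missed.

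**Conclusion.** The point holds conditionally. If Week k means k weeks after the infusion, which the follow-up wording in both documents favours, the SAP windows are one day early and a stated rule removes protocol-compliant PK samples from the by-visit summaries. If the site uses Study Day 7k, nothing is lost. The documents do not settle which applies, so the windows cannot be called a proven error.

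Under the first reading the expected loss ranges from zero to about 8 of 42 samples. The upper figure assumes uniform attendance, which nothing in the documents supports, so it should not be read as a forecast. At 5% attendance on the +2 day the loss is about 2.

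Where it occurs, the exclusion removes more information than it protects: a typical 5% shift in a visit mean, against about 1% from keeping the late sample. The damage is confined to concentration summaries and, probably, mean plots.

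**What to change.** Before database lock, confirm the nominal study day the site uses for each Week visit, state it in SAP 8.4.3, and align Tables 1 to 3 with it.

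- **If Week k is 7k days after dosing:** Day 13–17, 27–31, 41–45, 55–59, 69–73, 83–87 and 97–101.
- **If Week k is Study Day 7k:** keep the present windows and record the definition.
- **If it cannot be confirmed:** use Day 7k-2 to Day 7k+3, that is 12–17, 26–31, 40–45, 54–59, 68–73, 82–87 and 96–101.

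The tables should not be shifted without this check. If the site books Week 2 as Day 14, a move to Day 13–17 would exclude a compliant Day 12 visit, with the same loss at every later visit.

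A sentence should also say how a scheduled PD, laboratory, vital-sign or ADA value outside its window is assigned.

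The cost is a query to the site and a small SAP edit, which SAP 5.2 permits until database lock. The six-day window admits one extra day, worth about 3% in concentration at the stated half-lives, and adjacent visits still do not overlap.

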6.7.1.6 Unscheduled Visits

In the event of unscheduled visits, a non-exhaustive list of assessments and procedures which may be performed can be found in the schedule of events (Table 4).

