**Table 3** **Visit window of the other items**

Analysis time point	Visit Window	Laboratory a)	ADA	Physical Examination c)	12-lead ECG	Pregnancy Test d)
Screening	Within 21 days prior to IMP administration	X		X	X	
Day -1	Within Day -1	X		X		
Day 1	Preinfusion	Before IMP administration within Day 1		X	X	

Analysis time point		Visit Window	Laboratory a)	ADA	Physical Examination c)	12-lead ECG	Pregnancy Test d)
1 hr 2 hr 4 hr 8 hr 10 hr 12 hr	1 hr	0.75 hr to <1.25 hr					
	2 hr	1.75 hr to <2.25 hr					
	4 hr	3.5 hr to <4.5 hr	X			X	
	8 hr	7.5 hr to <8.5 hr					
	10 hr	9 hr to <11 hr					
	12 hr	11 hr to 13 hr					
Day 2	Within Day 2	X					
Day 3	Within Day 3	X					
Day 5	Within Day 5	X					
Day 8	Within Day 8	X					
Follow-up Week 2	Day 12 to Day 16	X					
Follow-up Week 4	Day 26 to Day 30	X					X
Follow-up Week 6	Day 40 to Day 44	X					
Follow-up Week 8	Day 54 to Day 58						X
Follow-up Week 10	Day 68 to Day 72	X b)					
Follow-up Week 12	Day 82 to Day 86						X
Study Completion Visit (Week 14) / Withdrawal (WD)	Day 96 to Day 100 or when the subject is withdrawn	X	X	X	X	X	

a) Laboratory includes hematology, chemistry, and urine and hematology measurements, taken under fasting condition except from screening.

b) Only hematology and chemistry.

c) A full physical examination will be performed at screening and at Week 4 visit. At all other visits brief physical examinations will be performed, only if indicated.

d) Urine pregnancy test is to be performed with a dipstick at week 4, 8, 12 and study completion.

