### 15.3.1 Descriptive Statistics of Laboratory Parameters

Population: Safety Analysis population

Group: Emapalumab, Placebo

Contents:

- Calculate the descriptive statistics of quantitative laboratory parameters (in Table 7 in Section 15.3 Laboratory data) at each analysis time point (defined in Table 3 in Section 8.4.3 Visit Windows) by groups.
- Conduct the same analysis by treatment groups and grades (Low/Normal/High).
- Conduct the same analysis for change from baseline.

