### **15.3.4      Contingency Table of Laboratory Parameters**

Population: Safety Analysis population

Group: Emapalumab, Placebo

Contents: 

- Create cross tables of normal range grading (Low/Normal/High) of quantitative laboratory parameters (in Table 7 in Section 15.3 Laboratory data) of baseline and at each analysis time point after IMP administration (defined in Table 3 in Section 8.4.3 Visit Windows) by groups.
- Remove data from calculation if both data from before and after IMP administration do not exist.

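### Unscheduled post-dose laboratory values can miss the SAP's by-visit tables, and no table gives the per-subject incidence of abnormal values that the protocol promises

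*SAP*

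**What the plan says.** SAP 8.4.3 sets the scope of the windows: "The analysis time points, based on the visit windows, will be used for analysis". Within a window, "Priority will be given to scheduled visits; unscheduled visits will be used if no scheduled visits occurred within the analysis visit window". Further tie-breaks choose the value nearest the target day, then the earlier of two equidistant values. For repeats on one day, "In the case of 2 or more measurements on the same date, the earliest measurement will be selected".

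SAP Table 3 gives the laboratory windows. Days 2, 3, 5 and 8 are single days. Later windows are five-day blocks, for example "Day 12 to Day 16" for Week 2 and "Day 26 to Day 30" for Week 4. Nothing assigns the days between blocks to a time point.

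The laboratory tables rest on these time points. SAP 15.3.1 summarizes values "at each analysis time point (defined in Table 3 in Section 8.4.3 Visit Windows) by groups". SAP 15.3.4 plans a shift table: "Create cross tables of normal range grading (Low/Normal/High) of quantitative laboratory parameters", baseline against each time point. SAP 15.3.3 does the same for qualitative urinalysis. None has a row for any-time, lowest or highest post-baseline values.

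Protocol 6.7.1.6 foresees extra data: "In the event of unscheduled visits, a non-exhaustive list of assessments and procedures which may be performed". It points to the schedule of events (Table 4), which appears to include laboratory tests in the unscheduled-visit column. Protocol 8.3.4.2 commits to tabulating, by IMP group, how often abnormal laboratory values occur, and does not limit this to scheduled visits.

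**The concern.** Unscheduled tests are often taken because something is suspected, or to recheck an earlier result. A rule that mostly leaves them out of the tables tilts the tabulated laboratory picture towards normal. Laboratory parameters are a named secondary endpoint, and with so few subjects one abnormal value changes what a table says about an arm. A report written from the shift tables alone could state that no subject left the normal range when the listings show that one did.

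**Working it through.** There is no sample-size or power figure to reproduce. The check applies the SAP rule to the calendar and to example subjects.

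**Step 1. Days with a laboratory time point (SAP Table 3).** The count starts at Day 2, because Day 1 has only a window around 4 hours.

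- Hematology and chemistry: 4 single days, plus five blocks (Weeks 2, 4, 6, 10, 14) of 5 days. 4 + 5 × 5 = 29 of 99 days. Outside: 99 − 29 = 70, and 70/99 = 70.7%.
- Urinalysis: Week 10 is excluded by footnote b. 4 + 4 × 5 = 24 of 99 days. Outside: 99 − 24 = 75.

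Counting Day 1 as covered gives 30 and 25 of 100. The 70 and 75 days outside do not change.

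**Step 2. Example subjects.** The baseline and all scheduled values are Normal, and there is one unscheduled High value of a chemistry parameter.

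| Unscheduled High | Scheduled Week 4 visit | Shift table under the priority rule | If only the nearest-value rule applied |
|---|---|---|---|
| Day 20 | Day 28, Normal | Normal at every time point | Normal at every time point |
| Day 29 | Day 28, Normal | Normal at every time point | Normal at every time point |
| Day 28 | Day 26, Normal | Normal at every time point | High at Week 4 |
| Day 29 | missed | High at Week 4 | High at Week 4 |

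Two mechanisms act: gaps between windows (first line) and scheduled-first priority inside a window (second and third lines). The last line shows that exclusion is not absolute.

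**Step 3. Where an untabulated value can still appear.**

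- Listings: SAP section 8 and section 16.
- Individual plots at actual times: SAP 15.3.2, quantitative parameters only.
- Adverse event tables: SAP 15.2.1 to 15.2.4, which use no visit windows. Under protocol 6.7.7.1.1 an abnormal value qualifies only if it causes signs or symptoms, is judged clinically significant, needs treatment, or alters IMP administration.

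An out-of-range value that meets none of these conditions reaches no table.

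**Step 4. Effect of one such subject.** In the emapalumab arm the planned shift table shows 0 of 6 leaving Normal. A row that uses all values shows 1 of 6 = 16.7%. In placebo one subject is 1 of 2 = 50%. These figures reflect arm size and do not predict how often this will happen.

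**Step 5. Protocol 8.3.4.2 against the SAP.** By-visit counts are not an incidence per subject, even without unscheduled visits. One High at Week 2 and one High at Week 4 may be the same subject (1 of 6 = 16.7%) or two subjects (2 of 6 = 33.3%). The planned tables do not distinguish these.

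**The case against.** The strongest reply is that nothing is lost. Every endpoint is listed individually, quantitative laboratory values are plotted at actual times, and with 8 subjects and no hypothesis tests the listings can be read in full. Any laboratory abnormality judged clinically significant becomes an adverse event and is counted whenever it occurs. This stands. A reader might infer that the safety tables would hide an important abnormality. The documents do not support that, because what escapes tabulation is an out-of-range value that does not qualify as an adverse event.

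Second, the priority sentence follows wording about descriptive statistics, so it may not bind the shift tables. This matters only for the third line of the Step 2 table. The Day 20 and Day 29 examples survive, because the shift tables use only the SAP 8.4.3 time points.

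Third, a reader might take 70.7% as the chance that an unscheduled value is dropped. It is not. It is a share of calendar days for hematology and chemistry, it says nothing about when unscheduled visits occur, and the documents give no expected number.

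Fourth, it is tempting to extend the point equally to vital signs and ECG. Vital signs have no Normal/Abnormal table (SAP 15.5.1), so the shift-table consequence cannot arise there. As far as the extracted Table 4 can be read, no ECG is marked for unscheduled visits, although protocol 6.7.1.6 does not exclude one. The point is therefore confined to laboratory data.

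Finally, unscheduled values are not barred outright. One enters when its window has no scheduled visit, and an unscheduled pre-dose value can be the baseline under SAP 8.4.4.

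**Conclusion.** The point holds for laboratory data. Followed as written, the SAP tabulates an unscheduled post-dose laboratory value only when it falls in a window without a scheduled visit. The shift table can then show a subject as Normal throughout although an out-of-range value was recorded. Separately, the SAP has no table giving the per-subject incidence of abnormal laboratory values that protocol 8.3.4.2 promises.

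The size is modest: a tabulation gap in a secondary endpoint, with the source data kept and clinically significant values counted as adverse events. It has practical effect only if unscheduled laboratory tests occur, and their number could be zero. The missing incidence table does not depend on that. The conclusion assumes that the listings and the actual-time plots include unscheduled values, which is the natural reading but is not stated. It is worth correcting before database lock, by which SAP 5.2 requires any revision to be final.

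**What to change.** Keep the by-visit rule, and state in SAP 8.4.3 that the window and priority rules apply to by-visit summaries only. Then add rows that use all post-dose values, scheduled and unscheduled:

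- **SAP 15.3.4:** for each quantitative laboratory parameter, baseline category against lowest post-baseline category, and baseline category against highest. Two rows are needed because a single worst category is undefined for a parameter that can be both Low and High. A subject who is both is counted in each.
- **SAP 15.3.3:** for each qualitative urinalysis parameter, baseline against highest post-baseline category.
- **Optional:** equivalent rows for ECG, and minimum and maximum post-baseline values for vital signs.

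These rows supply the incidence by category. They do not supply the severity and relationship breakdown that protocol 8.3.4.2 also mentions, so the SAP should say where those are given or why they are not.

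The cost is SAP wording and a few added rows, with no new data and no change to study conduct. The drawback is that the rows depend on how often each subject is tested, and a subject who is retested has more chances of an abnormal result. A footnote should say so.

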4.1.2.3 Clinical Data

Since the start of the clinical development program for emapalumab, more than 100 patients have received emapalumab in clinical trials and through compassionate use. Furthermore, more than 70 patients have been treated to date in the US following FDA approval, and post-marketing surveillance has not revealed any additional safety concerns with the use of emapalumab.

Emapalumab has been granted Orphan Drug Designation in the United States (US) on 26 March 2010 and in Europe (EU) on 09 June 2010. Emapalumab has obtained Breakthrough designation in US on 11 March 2016 and PRIME designation in EU on 26 May 2016.

On 20 November 2018 the FDA approved emapalumab for the treatment of adult and pediatric (newborn and older) patients with pHLH with refractory, recurrent or progressive disease or intolerance with conventional HLH therapy.

The FDA approval was based on data from study NI-0501-03, interim data from the pivotal study NI-0501-04 and interim data from the long-term follow-up study NI-0501-05.

Study NI-0501-03 was a phase 1 randomized double-blinded placebo-controlled single ascending dose study, in 20 healthy adult volunteers investigating the safety, tolerability and pharmacokinetic (PK) profiles of single intravenous (IV) administrations of emapalumab took place between September 2011 and January 2013. During this study, 6 subjects received placebo, while 3, 3, 4, and 4 subjects (in total 14 subjects) received emapalumab doses of 0.01, 0.1, 1, and 3 mg/kg, respectively.

Emapalumab PK data from healthy volunteers were evaluated using a population modeling approach. The PK of emapalumab was best described by a two-compartment model (NI-0501-03 - Modelling and Simulation support to NI-0501 PK analysis of study NI-0501-03). In healthy volunteers, emapalumab has the typical PK profile expected for a mAb, with low central and peripheral volumes of distribution (3.02 L and 2.83 L), slow clearance (0.007 L/h) and long distribution and terminal half-lives (1.55 and 25.4 days).

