**Table 2** **Visit Window of Vital Signsb)**

Analysis time point	Visit Window	
Screening	Within 21 days prior to IMP administration	
Day -1	Within Day -1	
Day 1	1 hr	0.75 hr to <1.25 hr
	1.5 hr	1.25 hr to <1.75 hr
	2 hr	1.75 hr to <2.25 hr
	2.5 hr	2.25 hr to <2.75 hr
	3 hr	2.75 hr to <3.25 hr
	3.5 hr	3.25 hr to <3.75 hr
	4 hr	3.75 hr to <4.5 hr
	5 hr	4.5 hr to <5.5 hr
	6 hr	5.5 hr to <6.5 hr
	7 hr	6.5 hr to <7.5 hr
	8 hr	7.5 hr to <8.5 hr
	9 hr	8.5 hr to <9.5 hr
Day 2	10 hr	9.5 hr to <11 hr
	12 hr	11 hr to <13 hr
Day 2	Within Day 2	
Day 3	Within Day 3	
Day 5	Within Day 5	
Day 8	Within Day 8	
Follow-up Week 2	Day 12 to Day 16	
Follow-up Week 4	Day 26 to Day 30	
Follow-up Week 6	Day 40 to Day 44	
Study Completion Visit (Week 14) / Withdrawal (WD)	Day 96 to Day 100 or when the subject is withdrawn	

b) Body weight and height will be collected at Screening, and body weight at Study Day -1 and Study Completion Visit (Week 14)/ Withdrawal (WD).

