## **14 Pharmacokinetic and pharmacodynamic assessment**

### **14.1 Pharmacokinetic assessment**

PK parameters will be calculated using the actual time and actual dose of study drug of collected samples. Sample collected before administration will be analyzed as time point 0 hours. Linear Trapezoidal Linear Interpolation will be used to calculate AUC and AUMC, by using actual elapsed time values. Data points BLOQ in the end of the serum concentration time curve will be omitted from estimation of AUC and AUMC using Phoenix WinNonlin.

The list of pharmacokinetic parameters derived in this study are presented in Table 4.

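### The ±5 min window for the 2 h PK sample can drop a valid, timed concentration from the 2 h summary to avoid a timing difference of about 0.3%

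*SAP*

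**What the plan says.** SAP 8.4.3, Table 1, sets the analysis windows for PK and PD samples. The 2 h window is "1 hr 55 min to < 2 hrs 5 min", that is ±5 min. The 4 h window is "3.75 hr to <4.25 hr" (±15 min), the 8 h and 10 h windows are ±30 min, Days 2 to 8 take the whole calendar day, and Week 2 takes "Day 12 to Day 16". No window covers 2 h 5 min to 3.75 h, so a sample at 2 h 8 min belongs to no analysis time point. No reason is given for ±5 min at 2 h.

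SAP 14.1 states the consequence: when a blood sample falls outside its window, "the relevant serum concentration will be listed but excluded from the calculation of summary statistics". The same section also says that "PK parameters will be calculated using the actual time and actual dose of study drug of collected samples", and SAP 14.1.3 draws the individual profiles at actual times.

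Protocol Table 4 gives ±2 days for follow-up visits and no tolerance in minutes for Day 1. Protocol 6.7.5 names the nominal Day 1 times and requires the date and time of sampling to be recorded.

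**The concern.** Emapalumab is a slowly cleared antibody: protocol 4.1.2.3 reports "long distribution and terminal half-lives (1.55 and 25.4 days"). Once the infusion has ended, a few minutes make almost no difference to the concentration. A sample a few minutes outside the 2 h window has a known time and a valid assay result, yet it drops out of the 2 h mean, SD, geometric mean and CI.

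Only six subjects receive emapalumab, so each lost value matters to a summary of that size. At stake is the precision of one row of the concentration table (SAP 14.1.1) and one point on the mean ± SD curve (SAP 14.1.2). Protocol 4.2 plans to compare these PK results with the earlier non-Japanese study.

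**Working it through.** **Inputs.** Protocol 4.1.2.3: V1 = 3.02 L, V2 = 2.83 L, CL = 0.007 L/h, half-lives 1.55 and 25.4 days. Protocol 6.1: 1 h infusion. Protocol 6.6.4: infusion may be extended to 2 h. Protocol 8.1: CV within 30% for Cmax and AUC. SAP 4.3: six emapalumab subjects. Dose and body weight cancel in percentage changes.

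**Step 1: complete the model and reproduce the protocol's figure.** Intercompartmental clearance Q is not stated. With k10 = CL/V1, k12 = Q/V1 and k21 = Q/V2, the rate constants are

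α, β = ½[(k10 + k12 + k21) ± √((k10 + k12 + k21)² − 4·k10·k21)].

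Setting ln 2/α to 1.55 days gives Q = 0.0255 L/h, k10 = 0.00232, k12 = 0.00843, k21 = 0.00900, α = 0.01863 and β = 0.00112 per h. The terminal half-life is then ln 2/β = 25.8 days, against 25.4 stated (1.6% off).

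**Step 2: change around 2 h after a completed 1 h infusion.** The weights are (α − k21)/(α − β) = 0.550 and (k21 − β)/(α − β) = 0.450. The early fractional rate of fall is about 0.550 × 0.01863 + 0.450 × 0.00112 = 0.0108 per h, so 15 min costs about 0.0108 × 0.25 = 0.27%. The full infusion formula gives:

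| Actual time | Change from 2:00 |
|---|---|
| 2:05 | −0.09% |
| 2:15 | −0.27% |
| 3:00 | −1.05% |

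Sensitivity: if Q is solved from the 25.4-day half-life instead, the 15 min fall is about 0.33%. If the whole profile fell with the 1.55-day half-life, it would be 1 − exp(−0.01863 × 0.25) = 0.46%.

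**Step 3: what Table 1 accepts elsewhere (same model).**

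| Time point | Window | Timing difference |
|---|---|---|
| 4 h | ±15 min | about 0.26% |
| 8 h | ±30 min | about 0.51% |
| Day 2 | calendar day | about 19% from 15 h to 39 h (assuming a 09:00 infusion) |
| Week 2 | ±2 days | +6.2% / −5.5% |

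**Step 4: cost of losing one of six values.** The CI half-width on the log scale is t/√n times the SD.

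- n = 6: 2.571/√6 = 1.049. n = 5: 2.776/√5 = 1.242. Ratio 1.18, whatever the CV.
- At 30% CV the log-scale SD is √ln(1 + 0.3²) = 0.294. The 95% CI of the geometric mean widens from 0.73–1.36 to 0.69–1.44 times the estimate.
- Typical move of the mean: 30% × √(1/5 − 1/6) = 5.5%. At 20% CV it is 3.7%, and at 10% CV 1.8%.
- Keeping the value when it is 15 min late moves the mean of six by 0.27%/6 = 0.04%.

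**Step 5: where tight timing does matter.** With an infusion extended to 2 h, the concentration is still rising before 2 h. A sample 15 min early reads about 12% low and one 5 min early about 4% low; one 15 min late is still only 0.27% low. At the 1 h end-of-infusion sample, 5 min early means about −8%.

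**The case against.** The strongest answer is that little is lost. The primary PK endpoints are parameters, and these use actual times, so a 2 h 8 min sample still counts towards AUC, and towards Cmax if it is the peak. It also stays in the listing and the individual plots, and no hypothesis is tested. All of this stands. A reader might infer that the primary PK results are damaged; the documents do not support that.

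A reader might also infer that the tight window never reduces error. Step 5 shows otherwise for an early sample in an extended infusion, so an unconditional ±15 min could let in values about 12% low. That limits the remedy. It does not justify ±5 min on the late side.

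Nor do the documents show that losses are likely when an infusion is slowed. Protocol Table 4 times the 2 h sample from the start of infusion, so a slower infusion does not by itself move it. Subjects are inpatients in one Phase I unit, and no rate of missed times is given.

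It cannot be said for certain that a 2 h 8 min sample complies with all study instructions. Protocol 6.7.5 refers collection procedures to a laboratory manual that is not among the documents and may set a tolerance.

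Finally, windows that widen with elapsed time are an ordinary scheme. The 2 h vital-sign window, "1.75 hr to <2.25 hr", is a weak benchmark because those windows adjoin in order to allocate frequent readings. That is fair. The case rests on the rate of fall, which is nearly the same at 2 h and 4 h.

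**Conclusion.** The point holds, as a minor one. For a sample drawn after the infusion has ended, ±5 min at 2 h guards against a timing difference of about 0.3% (0.27 to 0.46% across the assumptions tried). If one of six values is excluded as a result, the CI of the 2 h mean is 18% wider and, at 30% CV, the mean typically moves by about 5.5%. The effect is confined to the 2 h concentration summary and, by implication, the mean curve.

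This rests on four assumptions: Q solved from the stated figures, the earlier study's model applying to Japanese subjects, the 30% CV for Cmax and AUC carrying over to the 2 h concentration, and the windows in the exclusion rule being those of Table 1. The probability of losing a value is unknown, so the 18% and 5.5% are conditional on a loss.

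**What to change.** In SAP 8.4.3 or 14.1, before database lock, add one of the following:

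- accept the 2 h PK concentration within ±15 min, provided it was drawn after the actual end of infusion; or
- keep any timed post-infusion Day 1 PK sample in the summary at its nearest nominal time, with a flag.

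Leave the 1 h end-of-infusion window out of this change. Because Table 1 uses one cell for PK and PD, state whether the wider window also applies to the 2 h PD sample. The cost is one table cell or one sentence, and a timing difference of about 0.3% in any value that is kept.
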